5.2.2 Optisure Lead Related Events

Adverse Events related to the Optisure lead will be classified and reported as complications or observations. RV lead related complications or observation are defined in section 5.2.1

5.3 Sub-study - Outcome Measures

5.3.1 The annual hazard rate of lead electrical dysfunction

Lead Population

All enrolled Optisure leads being followed in this sub-study.

Analysis:

The annual hazard rate will be assessed.

5.3.2 The annual hazard rate of externalized conductors (from enrollment)

Lead Population

All enrolled Optisure leads being followed in this sub-study.

Analysis:

The annual hazard rate will be assessed.

5.3.3 The annual hazard rate of other visual lead anomalies by each subcategory (from enrollment)

Lead Population

All enrolled Optisure leads being followed in this sub-study.

Analysis:

The annual hazard rate will be assessed.

5.3.4 Prevalence of “other insulation anomalies” in “returned leads” (as defined in section 2.0)

Lead Population

Any enrolled lead in the sub-study that is returned to St. Jude Medical for analysis.

Analysis:

The prevalence of “other insulation anomalies” will be calculated as the number of returned leads that have “other insulation anomalies” divided by the total number of returned leads in enrolled sub-study patients. The one-sided 95% UCB for prevalence will be calculated using Clopper-Pearson exact method.

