2.0 Purpose

The purpose of this post approval study is to characterize the chronic performance of the SJM Optisure family of HV leads in patients that have an approved indication, as per ACC/AHA/HRS/ESC guidelines, for implantation of an ICD or CRT-D system for treatment of heart failure or life-threatening ventricular tachyarrhythmia, and who meet all the inclusion/exclusion criteria. The Optisure lead study will be performed in compliance with the Conditions for Approval as agreed upon with the FDA. If during the course of the study a future generation of the Optisure RV lead is approved, these devices may be included in the study upon agreement with the FDA.

The following objectives will be evaluated in the post approval study:

1. To determine the Optisure lead related complication free rate at 5 years
2. To document all Optisure lead related adverse events

Additionally, the following objectives will be evaluated in a subset of patients in the Optisure lead study who agree to participate in a sub-study:

1. To determine the incidence of externalized conductors after enrollment
2. To determine the incidence of other visual lead anomalies by each subcategory per Appendix A after enrollment
3. To determine the incidence of electrical dysfunction[§] after enrollment
4. To evaluate the 30-day adverse event rate associated with lead revision procedures (include lead extractions or abandonments with or without lead replacement)
5. To determine the prevalence of “other insulation anomalies” in returned Optisure leads:
 - Internal abrasion short under RV shock coil
 - Internal abrasion short under SVC shock coil
 - Exposed conductors defined as a breach of the outer insulation and/or breach of the internal silicone lumen tubing, but the conductor cable is contained within the lead body diameter.

[§]”Electrical dysfunction” is determined to be present after adjudication of the following cases of potential electrical failures that led to the lead being either surgically capped/extracted or electrically abandoned. Potential electrical failures include the following:

- Presence of non-physiologic noise not due to external interference
- Rise in pace/sense (p/s) conductor impedance to $> 2000 \Omega$ or increase of more than 200Ω over previous 6 months or increase of 400Ω over any period of time
- Decrease of more than 200Ω over previous 6 months or to impedance $< 200 \Omega$ from baseline impedance $> 300 \Omega$ or decrease of 400Ω over any period of time

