9.3 System Revisions – if applicable

If the system revision procedure occurs more than 3 months after implant then obtain cinefluoroscopy views of the entire length of the implanted leads before repositioning or explanting the Optisure lead. Cinefluoroscopy should be performed in three views (AP, LAO 45° or the best possible LAO view, RAO 45° or the best possible RAO view) and submitted to St. Jude Medical. If the patient is unwilling then the imaging is not required.

For all lead revisions (e.g. replacement or repositioning of the lead) complete the applicable testing as outlined in section 9.2.1. Any explanted pulse generator or leads (including damaged leads, lead segments and lead fragments) should be returned to St. Jude Medical for analysis promptly.

Any changes to the status of a lead (i.e., capped, removed) will be documented on the Product Out of Service Case Report Form. Complete an Adverse Event (if applicable), System Revision, Imaging (if applicable), and Out of Service for any product used but not implanted (e.g. contaminated, dropped or opened in error) Case Report Form. Submit the forms to St. Jude Medical using the EDC system.

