17.0 Returning Devices and Leads to St. Jude Medical

St. Jude Medical strongly encourages physicians to notify our Patient Records department ([name]) each time a device or lead is removed from service for any reason. Additionally, all explanted products are requested to be returned to St. Jude Medical for laboratory evaluation whether or not a malfunction is suspected. To facilitate the return of explanted devices and leads, St. Jude Medical offers a no-cost Returned Products Kit comprised of a postage paid explant box with a shipping address label, a removed device information form, a biohazard bag, and biohazard labels to seal the explant box. This kit, #N0004, can be ordered free of charge by contacting St. Jude Medical Customer Service ([name]).

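### Section 5.3.4 estimates insulation anomalies from sub-study returned leads only, although explanted leads are requested from every enrolled patient; adding the rest would gain precision at little cost

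*Protocol*

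**What the plan says.** Section 2.0 lists the prevalence of other insulation anomalies "in returned Optisure leads" as the fifth of a set introduced by the words "the following objectives will be evaluated in a subset of patients in the Optisure lead study who agree to participate in a sub-study". The anomalies are internal abrasion shorts under the RV or SVC shock coil, and exposed conductors that remain within the lead body.

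Section 5.3.4 carries the limit into the analysis twice. The population is "Any enrolled lead in the sub-study that is returned to St. Jude Medical for analysis", and the count of leads with an anomaly is "divided by the total number of returned leads in enrolled sub-study patients". The precision statement is: "The one-sided 95% UCB for prevalence will be calculated using Clopper-Pearson exact method".

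The return of hardware is not limited to the sub-study. Section 9.3, on system revisions, says: "Any explanted pulse generator or leads (including damaged leads, lead segments and lead fragments) should be returned to St. Jude Medical for analysis promptly". Section 14.0 asks for the same after a death. Section 17.0 says that "all explanted products are requested to be returned to St. Jude Medical for laboratory evaluation whether or not a malfunction is suspected".

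The reporting list in section 6.1 names this prevalence in returned Optisure leads without mentioning the sub-study; the item just before it, on electrical dysfunction, does mention it.

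**The concern.** Most section 5.3 measures of visible lead damage depend on cinefluoroscopy at 24, 36, 48 and 60 months, which only sub-study patients undergo. Restricting those measures to the sub-study is unavoidable. The measure in 5.3.4 is different: it is taken on leads sent back for analysis, and the protocol requests those from every patient. Limiting numerator and denominator to sub-study patients leaves out leads that the sponsor has already asked to receive, and the protocol gives no reason for doing so.

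Precision is at stake. Returned leads are likely to be few, and an exact upper bound on a few dozen leads or fewer is wide. A report of no internal abrasion shorts would then say little about how common they might be, even among returned leads.

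**Working it through.** **The plan's own sizes.** Attrition (sections 4.3 and 5.2.1): 1 − (1 − 0.38)(1 − 0.22) = 0.516, stated as 52%. Sub-study: 200 / 0.48 = 416.7, giving 417. Main study: 828 / 0.48 = 1725. Both figures reproduce.

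**Share of patients.** 417 / 1725 = 24.2% are in the sub-study and 1308 / 1725 = 75.8% are outside it. The enrolled base differs by a factor of 1725 / 417 = 4.1.

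**Upper bound.** The one-sided 95% Clopper-Pearson bound for x anomalies in n leads is the 0.95 quantile of a Beta(x + 1, n − x) distribution. For x = 0 this is 1 − 0.05^(1/n).

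**Number of returned leads.** The protocol gives none, so a range is assumed, with the same return fraction inside and outside the sub-study (exact halves rounded down):

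| Assumed fraction returned | Leads, sub-study vs all | Bound with zero anomalies, sub-study vs all | Ratio |
|---|---|---|---|
| 2% | 8 vs 34 | 31.2% vs 8.4% | 3.7 |
| 5% | 21 vs 86 | 13.3% vs 3.4% | 3.9 |
| 10% | 42 vs 172 | 6.9% vs 1.7% | 4.0 |

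**A count tied to the plan's complication rate.** Assume instead one returned lead per lead complication, with 95% complication-free survival and 48.4% retention at five years, both exponential. Then λ = −ln(0.95)/5 = 0.0103 and μ = −ln(0.484)/5 = 0.1451. The fraction with an observed complication is λ/(λ + μ) × (1 − e^(−5(λ + μ))) = 0.0357. That gives 0.0357 × 417 = 14.9 and 0.0357 × 1725 = 61.5, or about 15 and 62 leads. The zero-anomaly bounds are 18.1% and 4.7%, inside the range of the table.

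**Non-zero anomalies.** A fair comparison keeps the prevalence similar, not the count. One anomaly in 15 leads (6.7%) has a bound of 27.9%. Four in 62 (6.5%) has a bound of 14.2%. The gain is about twofold.

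**Unequal return.** If sub-study leads were returned 1.5, 2 or 3 times as often as the others, the share of returned leads lying outside the sub-study, 1308 / (1308 + 417k), would be 68%, 61% or 51%.

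**The case against.** The strongest reply is that nothing here is wrong. Section 2.0 places the objective in the sub-study, section 5.3 is headed as sub-study outcomes, and 5.3.4 follows both. The measure is descriptive, with no hypothesis or precision target to miss. All of that stands: this is a choice that could be better, not a contradiction between 2.0 and 5.3.4.

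A reader might infer that section 6.1 intends the wider population because its item carries no sub-study label. That is weak evidence. The same list gives the percentages with externalized conductors at 24, 36, 48 and 60 months without a label, and that scheduled imaging is done only in the sub-study.

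A reader might also infer that three quarters of the available data are discarded. The documents do not support this. The 75.8% is a share of enrolled patients, and the share of returned leads is unknown. Leads from outside the sub-study are still requested for analysis, and insulation damage that counts as a lead-related complication enters the whole-study measures in 5.1.1 and 5.2.1.

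The complication-based count is a rough proxy. It may be too high, because leads can be repositioned or capped and perforations count as complications even without intervention. It may be too low, because it omits explants for infection or transplant and after death. At the plan's 38% mortality there would be about 158 sub-study deaths; if leads came back after 10% or 20% of them (assumed), the sub-study would have about 31 or 47 leads and zero-anomaly bounds of 9.2% or 6.2%. This changes the absolute bounds. The advantage of the larger base remains as long as leads from outside the sub-study are also returned in reasonable numbers.

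**Conclusion.** The point holds as a cheap improvement. Section 5.3.4 draws on 24% of enrolled patients for a measure that needs none of the sub-study's imaging, while the protocol requests explanted leads study-wide. With equal return fractions of 2% to 10%, the zero-anomaly upper bound is about four times as high as it need be; at a similar non-zero prevalence it is about twice as high. These sizes rest on assumed return counts and on equal return in the two groups.

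It would go too far to conclude that the study cannot exclude a high rate of internal abrasion shorts in implanted leads because of this restriction. Returned leads are a selected group, and enlarging that group sharpens the estimate for returned leads only.

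**What to change.** In section 5.3.4, report the prevalence of other insulation anomalies and its one-sided 95% upper bound for all returned Optisure leads from enrolled patients, and show the pre-specified sub-study leads as a subset. State the same population in sections 2.0 and 6.1, so that one denominator is used throughout.

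No new visits, imaging or return requests are needed. The same laboratory classification into the three anomaly types must be tabulated for leads from outside the sub-study, which the protocol does not now say. Because the study runs under conditions agreed with FDA, changing the outcome population may need FDA agreement. The consent forms are not available here, so their wording should be checked. The report should say that the estimate describes returned leads, not all implanted leads.

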5.3.5 Time from externalized conductors to electrical dysfunction

Lead Population

All Optisure leads with externalized conductors but without electrical dysfunction.

Analysis:

Time to electrical dysfunction will be analyzed using the Kaplan-Meier method. The zero time will be the date at which externalized conductor was detected. Those patients who experience an externalized conductor after enrollment, but do not experience an electrical dysfunction will be censored 3 years after enrollment in this trial.

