4.3 Sub-Study Design and Scope

This sub-study will determine the incidence of externalized conductors and other visual lead anomalies (as evidenced by imaging) and the risk of progression to electrical dysfunction in patients implanted with an Optisure HV lead. A minimum of 200 subjects who consent to participate in this sub-study will undergo cinefluoroscopy (AP, LAO 45° or the best possible LAO view, RAO 45° or the best possible RAO view) at the 24, 36, 48 and 60 month follow-up visits.

Expected Attrition in patients with high voltage leads

Withdrawals due to death

[figure not shown]
Assuming an annual mortality of 7% in the ICD patient population, the mortality at 5 years is 30% $[1 - (1-0.07)^5]$ In the recent RHYTHM ICD/QuickSite 1056K left heart lead study using CRT-D devices, the annual mortality was 12.8%, which would result in a mortality of 49% $[1 - (1-0.128)^5]$ at 5 years. If the ICD:CRT-D device mix is 60%:40% then the expected overall mortality in this study at 5 years is 38% ($=0.6 \times 0.30 + 0.4 \times 0.49$).

Withdrawals due to reasons other than death

In an ongoing St. Jude Medical post-approval study consisting of CRT devices and LV leads, 102 patients have been withdrawn for reasons other than death during an average of 22 months of follow-up. This translates to an attrition of 22% over 5 years.

Assuming that deaths and withdrawals are independent events, the total attrition is expected to be approximately 52% ($= 1 - (1 - 0.38) \times (1 - 0.22)$) over 5 years. With an expected attrition at 5 years to be 52%, a total of 417 subjects who consent to participate in this sub-study will be enrolled in order to have at least 200 subjects with fluoroscopy data available at the 60 month follow-up visit.

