5.3.6 Time from other visual lead anomalies by each subcategory to electrical dysfunction

Lead Population

All Optisure leads with other visual lead anomalies (by each subcategory) but without electrical dysfunction.

Analysis:

Time to electrical dysfunction will be analyzed using the Kaplan-Meier method. The zero time will be the date at which other visual lead anomaly (by each subcategory) was detected. Those patients who experience other visual lead anomaly (by each subcategory) after enrollment, but do not experience an electrical dysfunction will be censored 3 years after enrollment in this trial.

5.3.7 Adverse Event rate through 30 days post-intervention for lead (e.g. extraction, abandonment, revision, other)

Lead Population

All Optisure leads that require an intervention/revision (e.g. extraction, abandonment, other).

Analysis

The 30-day adverse event rate will be calculated as the number of adverse events within 30 days associated with lead related interventions divided by total lead related interventions.

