5.3.8 Time from externalized conductors to clinical intervention

Lead Population

All Optisure leads with externalized conductors.

Analysis:

Time to clinical intervention will be analyzed using the Kaplan-Meier method. The zero time will be the date at which externalized conductor was detected. Those patients who experience externalized conductor after enrollment but do not experience clinical intervention will be censored 3 years after enrollment in this trial.

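### Sections 5.3.5 and 5.3.6 keep removed or capped leads, deceased patients and withdrawn patients at risk until a fixed 3-year date, which modestly lowers the estimated risk of progression to electrical dysfunction

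*Protocol*

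**What the plan says.** Section 4.3 of the protocol gives as one aim of the sub-study "the risk of progression to electrical dysfunction in patients implanted with an Optisure HV lead". Sections 5.3.5 and 5.3.6 carry that analysis.

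- **Estimator (5.3.5):** "Time to electrical dysfunction will be analyzed using the Kaplan-Meier method".
- **Time zero (5.3.5):** "The zero time will be the date at which externalized conductor was detected".
- **Censoring (5.3.5):** "Those patients who experience an externalized conductor after enrollment, but do not experience an electrical dysfunction will be censored"; the date is fixed at 3 years from enrollment.
- **Censoring (5.3.6):** "Those patients who experience other visual lead anomaly (by each subcategory) after enrollment, but do not experience an electrical dysfunction will be censored 3 years", again counted from enrollment.

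The population in both sections is leads, but the censoring sentence speaks of patients. Sections 5.3.8 and 5.3.9 use the same 3-year date for clinical intervention (5.3.8: "Time to clinical intervention will be analyzed using the Kaplan-Meier method").

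Three other places bear on this:

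- **Section 2.0** defines electrical dysfunction as an adjudicated electrical failure that led to the lead being capped, extracted or electrically abandoned.
- **Section 16.0** counts as withdrawal death, loss to follow-up, and removal or capping of the lead where no other Optisure lead replaces it.
- **Section 5.1.1** censors at withdrawal, but states this for the primary outcome only.

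**The concern.** An electrically intact lead taken out because of its appearance is not an event under Section 2.0 and cannot become one later. The same holds after death. A patient who has withdrawn may still have the event, but the study will not see it. The protocol expects all of these: 5.3.7 to 5.3.9 analyse interventions, and Section 4.3 plans for 38% mortality and 22% other withdrawal over 5 years.

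Under the written rule such leads stay in the Kaplan-Meier denominator, event-free, until the fixed date. The more often anomalous leads are removed early, the flatter the curve, and a reader may take that for benign lead behaviour. This is a stated rule with a definite result, not a detail left open.

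**Working it through.** **1. The plan's own attrition figures.** Mortality: 0.6 × 0.30 + 0.4 × 0.49 = 0.376, stated as 38%. Total attrition: 1 − 0.62 × 0.78 = 0.516, stated as 52%. Sub-study size: 200 / 0.48 = 416.7, stated as 417. All reproduce.

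**2. Death hazard.** −ln(1 − 0.38)/5 = 0.0956 per year.

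**3. Which leads the rule can affect.** Scheduled imaging is at 24, 36, 48 and 60 months. From detection to the 3-year cut-off leaves about 12, 0, −12 and −24 months. Visit windows (±90 days, Table 4) and enrollment up to 30 days after implant can add at most about 120 days for an early 36-month scan. So leads are carried after removal or death essentially only if the anomaly was found at the 24-month visit or on earlier unscheduled imaging. At 48 and 60 months the cut-off precedes time zero. That is a separate fault of the same sentence.

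**4. Size over 12 months.** The documents give no dysfunction hazard λ for anomalous leads and no elective removal rate r. Assume λ = 0.10 per year, and let c = 0.0956 + r.

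- Net risk = 1 − exp(−λ) = 9.5%.
- Literal rule = λ/(λ + c) × [1 − exp(−(λ + c))].

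| r per year (assumed) | λ + c | Literal rule | Gap to net risk |
|---|---|---|---|
| 0 (deaths only) | 0.1956 | 9.1% | 0.4 points |
| 0.1 | 0.2956 | 8.7% | 0.9 points |
| 0.2 | 0.3956 | 8.3% | 1.3 points |
| 0.4 | 0.5956 | 7.5% | 2.0 points |

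For λ between 0.05 and 0.20 the ratio of literal to net hardly changes: about 0.95 with deaths only and 0.91 with r = 0.1.

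**5. Crude incidence.** The literal formula in step 4 is itself the crude cumulative incidence with death and removal as competing events. A simulation (200,000 leads, λ = 0.10, r = 0.3) agrees: literal Kaplan-Meier 7.93%, Aalen-Johansen 7.93%, Kaplan-Meier censored at removal or death 9.57%.

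**6. Withdrawal.** Withdrawn patients are different, because later events are possible but unseen. The plan's 22% gives −ln(0.78)/5 = 0.0497 per year. With deaths and no elective removal, the literal rule gives 0.10/0.2453 × [1 − exp(−0.2453)] = 8.9%, against a crude incidence of 9.1%. So the rule is too low even for crude incidence, by about 0.2 points. This is an upper indication, since Section 5.2.1 includes some system explants in the 22%.

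**7. Informative removal.** In one simulated case, 30% of leads had λ = 0.30 and r = 1.0, and the rest λ = 0.05 and r = 0.1. True net risk was 11.1%, the literal rule gave 7.9%, and censoring at removal or death gave 9.4%. Ending time at risk removes part of the gap, not all.

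**The case against.** The strongest reply is that the rule is not wrong for every quantity. For deaths and removals, carrying the lead to a fixed date gives crude cumulative incidence exactly, and crude incidence is a legitimate target. This stands: the understatement is relative to net risk, and the protocol names no estimand. It does not cover withdrawn or lost patients, for whom the rule is low on either reading.

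A second reply is that Section 16.0 treats death and lead removal as withdrawal, so time at risk would stop there in practice. But censoring at withdrawal is written only for the primary outcome, and 5.3.5 and 5.3.6 state a different date. Nor is removal a withdrawal when another Optisure lead replaces the one removed. The patient then stays enrolled, and a rule that censors patients can keep the removed lead at risk.

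Third, the adjudication in Section 19.2 covers all sub-study leads taken out of service, so removals for a qualifying electrical failure are events and are not hidden. This also stands. The point concerns only leads removed without dysfunction.

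Fourth, progression is not among the five numbered sub-study objectives in Section 2.0, and no hypothesis rests on these curves. That limits the weight of the point. Section 4.3 nevertheless names progression, and the rule is explicit.

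**Conclusion.** The point holds, with modest size. Under the written cut-off, 12-month net risk of 9.5% would be shown as 9.1% with deaths only and as 7.5% with removal at 0.4 per year. These figures assume constant, independent hazards. Only the death hazard comes from the plan; the dysfunction and removal rates are assumptions.

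A reader might infer three stronger things that the documents do not support.

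- **A shortfall of 6 to 12 points.** This follows if leads found at 24 months are tracked to month 60: with the same hazards over 3 years, net risk is 25.9% against 19.9%, 17.6% or 14.0% with removal at 0.1, 0.2 or 0.4 per year. The protocol stops at 3 years after enrollment, so this does not describe the current text. It shows what would follow if the date were reconciled with the 60-month follow-up and the rest of the rule kept.
- **An effect on every detected anomaly.** Scheduled detections from month 36 on have little or no time at risk under the rule.
- **A competing-risks curve as the cure.** It would return the same figures as the literal rule for death and removal (step 5).

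**What to change.** In 5.3.5 and 5.3.6, analyse by lead. End time at risk at the earliest of: removal, capping or abandonment without adjudicated electrical dysfunction (including when another Optisure lead takes its place); death; withdrawal; end of follow-up. Make this edit together with reconciling the 3-year date with the 60-month follow-up, because moving the date alone enlarges the effect.

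State the estimand. Report the dysfunction rate per lead-year in service (cause-specific) as the measure of lead behaviour, and note that removal may be informative. If crude risk is also wanted, add the Aalen-Johansen cumulative incidence with removal and death as competing events and only other withdrawal or loss censored. Say that it does not correct the understatement of net risk. Because Section 16.0 lists death and some removals as withdrawal reasons, the text must separate these from other withdrawals.

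In 5.3.8 and 5.3.9, end follow-up at death or withdrawal in the same way.

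Cost: wording, and slightly more analysis and reporting. Changes in lead status are already recorded on the Out of Service form (9.3), and deaths and withdrawals on their own forms (14.0, 16.0).
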